## Summary Table of Study Protocol

Title	Retrospective Cohort Study Evaluating Clinical Outcomes in Patients with Granulomatosis with Polyangiitis (GPA)/microscopic polyangiitis (MPA) Treated with Avacopan
Protocol version identifier	20230026, Version 1.0
Date of last version of the protocol	NA
EU Post Authorization Study (PAS) Register No	NA
Active Substance	TAVNEOS® (avacopan)
Medicinal Product	NA
Device	NA
Product Reference	NA
Procedure Number	NA
Joint PASS	NA

Research Question and Objectives	
Primary objectives
 

• To describe the demographics and disease-specific features of patients who are and are not prescribed avacopan for GPA/MPA.

• Among people prescribed avacopan, to describe the demographics and disease-specific features of patients who do and those who do not initiate avacopan.

• To describe the outcomes, including disease- and treatment-specific outcomes, of patients who use avacopan.

○ Proportion achieving discontinuation of glucocorticoids for treatment of GPA or MPA 1 month before Month 6 and disease remission within 6 months of avacopan initiation.

○ Proportion achieving sustained remission at Month 12, defined as remission at Month 6 and remission at Month 12, with no glucocorticoid treatment for GPA/MPA 1 month before Month 12, and no relapse between Months 6 and 12

 
Secondary objectives
 

• To investigate baseline factors associated with glucocorticoid discontinuation and relapse risk in patients who initiate avacopan.

• To evaluate the association of glucocorticoid use patterns with relapse risk in patients who initiate avacopan.

 
Exploratory objective
 

• To explore the outcomes, including disease- and treatment-specific outcomes, of patients who use avacopan for greater than 12 months.

Country(ies) of Study	United States
Author	PPD

### Proper Version Numbering and Dating

VERSIONING:

Protocol Version	Date of Protocol	Page Header Date
Original Protocol, Version 1.0	February 19, 2024	February 19, 2024

**Study Design Schema [Required]**

Data source          Mass General Brigham ANCA-associated vasculitis cohort
	
Index dates
 
 
• Analysis 1: Date of avacopan prescription or date of non-avacopan, non-glucocorticoid treatment prescription (i.e., immunosuppressive drugs specified in Appendix C)
 
• Analysis 2: Date of avacopan prescription (for both avacopan initiators and non-initiators)
 
• Analysis 3: Date of avacopan initiation
 

Additional details regarding inclusion/exclusion criteria, endpoints, and outcomes are described in Analysis-specific schema
	

[figure not shown]

Index date          Date of avacopan prescription or date of non-avacopan, non-glucocorticoid treatment prescription
	

Inclusion criteria
 
 
• Diagnosed with new or relapsing GPA or MPA on or after December 1, 2021, the first date of avacopan use at Mass General Brigham
 
• At least 18 years old on index date
 
 
Exclusion criteria
 
 
• A diagnosis of EGPA.
 
• GPA/MPA attributed to cocaine/levamisole.
 
• No treatment of GPA/MPA during the baseline or follow-up periods (i.e., not treated for their GPA/MPA).
 
	
Characteristics to be evaluated
 
 
• Demographic features (e.g., age, sex, race/ethnicity)
 
• GPA/MPA features (e.g., BVAS v3, organ involvement, new or relapsing disease)
 
• Comorbidities at index date (e.g., hypertension, hyperlipidemia, Charlson Comorbidity Index)
 
• Healthcare resource utilization up to 12 months prior to index date
 

**Analysis 2: Initiated Avacopan and Did Not Initiate Avacopan**

[figure not shown]
Baseline (12 Month Lookback from Index Date)

- Demographics
- Clinical Characteristics
- Other GPA/MPA Medication Exposures
- Healthcare Resource Utilization and Costs

Index date          Date of avacopan prescription (for both avacopan initiators and non-initiators)
	

Inclusion criteria
 
 
• Diagnosed with new or relapsing GPA or MPA on or after December 1, 2021, the first date of avacopan use at Mass General Brigham
 
• At least 18 years old on index date
 
• Prescribed avacopan
 
	
Characteristics to be evaluated
 
 
• Demographic features (e.g., age, sex, race/ethnicity)
 
• GPA/MPA features (e.g., BVAS v3, organ involvement, new or relapsing disease)
 
• Comorbidities at index date (e.g., hypertension, hyperlipidemia, Charlson Comorbidity Index)
 
• Healthcare resource utilization up to 12 months prior to index date
 
• Reason for not initiating avacopan
 

Exclusion criteria
 
 
• A diagnosis of EGPA.
 
• GPA/MPA attributed to cocaine/levamisole.
 
• No treatment of GPA/MPA during the baseline or follow-up periods (i.e., not treated for their GPA/MPA).
 
	

Index date Date of avacopan initiation
	
Primary outcomes to be evaluated
 
 
• Proportion achieving discontinuation of glucocorticoids for treatment of GPA or MPA 1 month before Month 6 and disease remission within 6 months of avacopan initiation.
 
• Proportion achieving sustained remission at Month 12, defined as remission at Month 6 and remission at Month 12, with no glucocorticoid treatment for GPA/MPA 1 month before Month 12, and no relapse between Months 6 and 12
 


Inclusion criteria
 
 
• Diagnosed with new or relapsing GPA or MPA on or after December 1, 2021, the first date of avacopan use at Mass General Brigham
 
• At least 18 years old on index date
 
• Prescribed avacopan
 
 
Exclusion criteria
 
 
• A diagnosis of EGPA.
 
• GPA/MPA attributed to cocaine/levamisole.
 
• No treatment of GPA/MPA during the baseline or follow-up periods (i.e., not treated for their GPA/MPA).
 
	
Additional endpoints to be evaluated
 
 
• Glucocorticoid exposure, glucocorticoid toxicity
 
• Disease activity, renal outcomes, ANCA titer changes
 
• Change in comorbidities/biomarkers (e.g., BMI, lipids, A1c)
 
• Healthcare resource utilization (analysis from MGH only)
 
• Patient reported outcome measures
 
• Adverse events attributed to avacopan, infection, relapse, mortality
 

## 2. List of Abbreviations

ACR: American College of Rheumatology

AIS: Aggregate Improvement Score

ALT: Alanine aminotransferase

ANCA: Anti-neutrophil cytoplasmic antibody

AST: Aspartate aminotransferase

BMI: Body Mass Index

BVAS v3: Birmingham Vasculitis Activity Score version 3

BWH: Brigham and Women's Hospital

CCF: Cleveland Clinic Foundation

CHCC: Chapel Hill Consensus Classification

CKD-EPI: Chronic Kidney Disease Epidemiology Collaboration

CPK: Creatinine phosphokinase

CT: Computed tomography

CWS: Cumulative Worsening Score

DBP: Diastolic blood pressure

DILI: Drug-induced liver injury

EDW: Electronic Data Warehouse

eGFR: Estimated glomerular filtration rate

ELISA: Enzyme linked immunosorbent assay

ER: Emergency room

EULAR: European Alliance of Associations for Rheumatology

GAD-7: General Anxiety Disorder-7

GC: Glucocorticoid

GPA: Granulomatosis with polyangiitis

GTI-MD: Glucocorticoid Toxicity Index – Metabolic Domain

HCRU: Healthcare Resource Utilization

HDL: High density lipoprotein

HPF: High powered field

ICD: International Statistical Classification of Disease and Related Health Problems

IQR: Interquartile range

LDL: Low density lipoprotein

MGB: Mass General Brigham

MGH: Massachusetts General Hospital

mHAQ: Modified Health Assessment Questionnaire

MPA: Microscopic polyangiitis

MPO: Myeloperoxidase

NDI: National Death Index

PHQ-8: Patient Health Questionnaire-8

PPPM: per patient per month

PR3: Proteinase 3

PROM: Patient Reported Outcome Measure

PROMIS: Patient Reported Outcomes Measurement Information System

Q1: Quartile 1

Q3: Quartile 3

RAPID3: Routine Assessment of Patient Index Data 3

RBC: Red blood cell

RPDR: Research Patient Data Registry

SBP: Systolic blood pressure

SD: Standard deviation

TC: Total cholesterol

USRDS: United States Renal Data System

#### 4. Abstract

##### Study Title

Retrospective Cohort Study Evaluating Clinical Outcomes in Patients with Granulomatosis with Polyangiitis (GPA)/microscopic polyangiitis (MPA) Treated with Avacopan

##### Study Background and Rationale

- Avacopan (brand, Tavneos®) is a complement 5a receptor (C5aR) antagonist available as 10 mg oral capsules, with a recommended dosage of 30 mg twice daily with food. Avacopan was studied in a phase 3, active-controlled study (ADVOCATE), which evaluated the safety and efficacy of avacopan to induce and sustain remission without a prednisone taper in patients with newly diagnosed or relapsing anti-neutrophil cytoplasmic antibody (ANCA)-associated vasculitis (GPA or MPA). The two primary endpoints were clinical remission at Month 6, defined as achieving a Birmingham Vasculitis Activity Score version 3 (BVAS v3) of 0 and not taking glucocorticoids to treat GPA or MPA within 1 month before Month 6, and sustained remission, defined as remission at Months 6 and 12 (BVAS v3 of 0 and not taking glucocorticoids to treat GPA or MPA within 1 month before Month 12), without relapse between Months 6 and 12.
- Based on evidence from this study that patients receiving avacopan had a significantly higher percentage (66%) of sustained remission of symptoms when compared to an active control group (55%), avacopan was approved by the US Food and Drug Administration (FDA) in October of 2021 for the treatment of adult patients with severe active GPA or MPA as an add-on to standard therapy including glucocorticoids (GC). Since its approval, avacopan has been adopted by several

international guidelines for the treatment of GPA or MPA as a part of strategies to reduce exposure to GC.

- This retrospective cohort study aims to describe the burden of GPA/MPA, patterns regarding avacopan utilization, and the healthcare utilization and clinical outcomes at 1, 3, 6 and 12 months in avacopan users from the Mass General Brigham (MGB) GPA/MPA registry and potentially from the Cleveland Clinic Foundation (CCF) (negotiations are ongoing).

### **Study Feasibility and Futility Considerations**

- There are 133 patients identified through January 2024 from within the Mass General Brigham system who have been prescribed avacopan and 112 have initiated avacopan. Additionally, since December 1, 2021 (the date of avacopan availability at MGB), there are 60 patients diagnosed with GPA/MPA in the MGB system who were not prescribed avacopan. Among those who have initiated avacopan, there have been 23 relapses. Glucocorticoid exposure has varied but the majority of patients have discontinued glucocorticoids within 2 months of avacopan initiation. There are only 2 patients in this cohort with missing status regarding avacopan initiation.

### **Research Question and Objective(s)**

This study aims to describe the demographic and disease-specific characteristics associated with avacopan prescription and initiation and the outcomes observed among patients who initiate avacopan in a real-world setting between December 1, 2021 and May 1, 2024. Our research questions, study objectives, and endpoints are as follows:

- What are the demographics and disease-specific features of patients who are and are not prescribed avacopan for GPA/MPA?
- What are the demographics and disease-specific features of patients who do and do not initiate avacopan after prescription?
- What are the outcomes, including disease-specific (e.g., disease activity, renal function) and treatment-specific (e.g., glucocorticoid toxicity, infection), among patients who initiate avacopan?

Objectives	Endpoints
------------	-----------

Primary	
To describe the demographics and disease-specific features of patients who are and are not prescribed avacopan for GPA/MPA	Descriptive analysis of baseline demographic and clinical characteristics
Among people prescribed avacopan, to describe the demographics and disease-specific features of patients who do and those who do not initiate avacopan	
 
• Demographic features (e.g., age, sex, race/ethnicity)
 
• GPA/MPA features (e.g., BVAS v3, organ involvement, new or relapsing disease)
 
• Comorbidities at index date (e.g., hypertension, hyperlipidemia, Charlson Comorbidity Index)
 
• Healthcare resource utilization up to 12 months prior to index date
 

Among patients who use avacopan, to describe the outcomes, including disease- and treatment-specific outcomes	
 
• Complete remission at Month 6
 
• Complete remission at Month 12
 
• Proportion who achieve discontinuation of glucocorticoids for treatment of GPA or MPA 1 month before Month 6 and disease remission (based on a BVAS v3 of 0) within 6 months of avacopan initiation, as defined in ADVOCATE
 
• Proportion who achieve sustained remission at Month 12.
 
• Cumulative glucocorticoid exposure
 
• Median daily glucocorticoid dose
 
• Glucocorticoid toxicity
 
• Glucocorticoid Toxicity Index – Metabolic Domain (GTI-MD)
 
• Change in A1c
 
• Change in BMI
 
• Change in lipids
 
• Renal parameters (estimated glomerular filtration rate [eGFR], proteinuria, hematuria)
 
• ANCA titers
 
• Pathology results
 
• Adverse Events
 
• Patient reported outcome measures (RAPID-3, mHAQ, PHQ-8, GAD-7, and PROMIS)
 

Secondary	
To investigate baseline factors associated with glucocorticoid discontinuation and relapse risk in patients who initiate avacopan	Descriptive analysis of baseline demographic and clinical characteristics 
 
• Demographic features (e.g., age, sex, race/ethnicity)
 

	
 
GPA/MPA features (e.g., BVAS v3, organ involvement, new or relapsing disease)
 
Comorbidities at index date (e.g., hypertension, hyperlipidemia, Charlson Comorbidity Index)
 
Healthcare resource utilization up to 12 months prior to index date
 

To evaluate the association of glucocorticoid use patterns with relapse risk in patients who initiate avacopan	
Relapse, defined as a return (after prior improvement) of vasculitis activity on the basis of at least one major BVAS/WG item, at least three minor BVAS v3 items, or one or two minor BVAS v3 items for at least two consecutive clinical visits (ADVOCATE definition). Relapses will be assessed after Month 1.
 
Patients who had an increase in the BVAS v3 of <3 and the absence of major BVAS/WG items define a minor relapse. All other patients are defined as a major relapse. (Miloslavsky et al. 2015)

To evaluate healthcare resource utilization during follow-up in patients who initiate avacopan	Per patient per month estimates of all-cause and GPA/MPA-related healthcare resource utilization (HCRU) including outpatient visits, hospitalization rates and length of stay, Emergency Room visits
Exploratory	
To evaluate baseline healthcare costs in patients who are and are not prescribed avacopan for GPA/MPA (analysis from MGH only)	Per patient per month costs of all-cause and GPA/MPA-related resource use associated with outpatient visits, hospitalizations, Emergency Room visits
To evaluate baseline healthcare costs in patients who do and those who do not initiate avacopan (analysis from MGH only)	
To evaluate healthcare costs during follow-up in patients who initiate avacopan (analysis from MGH only)	All-cause and GPA/MPA-related costs associated with outpatient visits, hospitalizations, Emergency Room visits
To explore the outcomes, including disease- and treatment-specific outcomes, of patients who use avacopan for greater than 12 months	
Descriptive analysis of demographic and clinical characteristics and outcomes
 
 
Demographic features (e.g., age, sex, race/ethnicity)
 
GPA/MPA features (e.g., BVAS v3, organ involvement, new or relapsing disease)
 
Comorbidities at index date (e.g., hypertension, hyperlipidemia, Charlson Comorbidity Index)
 
Healthcare resource utilization
 

- Glucocorticoid exposure, glucocorticoid toxicity
- Disease activity, renal outcomes, ANCA titer changes
- Change in comorbidities/biomarkers (e.g., BMI, lipids, A1c)
- Healthcare resource utilization (analysis from MGH only)
- Patient reported outcome measures
- Adverse events attributed to avacopan, infection, relapse, mortality

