## Follow-Up Dates (vary by analysis/outcome)

### Treatment Outcomes

- Date of avacopan discontinuation (for time from initiation to discontinuation)
- Date of glucocorticoid discontinuation and usage patterns, including dosage changes (for time from initiation to discontinuation)
- 6 months after avacopan initiation (for primary outcomes at Month 6)
- 12 months after avacopan initiation (for primary outcomes at Month 12)

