## Variables

The exposures of interest include:

- Analysis 1: Prescription and non-prescription of avacopan for newly diagnosed or relapsing GPA/MPA;
- Analysis 2: Initiation and non-initiation of avacopan among those prescribed avacopan;
- Analysis 3: Patients who initiate avacopan.

The outcomes of interest include:

- Analysis 1: Comparing baseline features among those prescribed and those not prescribed avacopan
- Analysis 2: Comparing baseline features of patients initiating and not initiating avacopan among those prescribed avacopan.
  - Features compared in Analysis 1 and 2, include: 1) Demographic features (e.g., age, sex, race/ethnicity); 2) GPA/MPA features (e.g., BVAS v3, organ involvement, new or relapsing disease); 3) Comorbidities at index date (e.g., hypertension, hyperlipidemia, Charlson Comorbidity Index); 4)

Healthcare resource utilization up to 12 months prior to index date; 5) reason for not initiating (Analysis 2 only)

- Analysis 3: outcomes among those who initiate avacopan, including:
  - 1) Glucocorticoid exposure; 2) Remission at Month 6 (BVAS v3 = 0); 3) Sustained remission at Month 12; 4) Glucocorticoid toxicity; 5) Disease activity; 6) Renal outcomes; 7) ANCA titer changes; 8) Healthcare resource utilization; 9) Healthcare costs (analysis from MGH only); 10) Adverse events attributed to avacopan; 11) Infection; 12) Relapse (defined as a return (after prior improvement) of vasculitis activity on the basis of at least one major BVAS/WG item, at least three minor BVAS v3 items, or one or two minor BVAS v3 items for at least two consecutive clinical visits); 13) Mortality; 14) Patient reported outcome measures (RAPID-3, mHAQ, PHQ-8, GAD-7, and PROMIS)

Covariates include: 1) Demographic features (e.g., age, sex, race/ethnicity); 2) GPA/MPA features (e.g., BVAS v3, organ involvement, new or relapsing disease); 3) Comorbidities at index date (e.g., hypertension, hyperlipidemia, Charlson Comorbidity Index)

All exposures, outcomes, and covariates are routinely collected via clinically-collected data at Mass General Brigham, as stored in the electronic health record and/or electronic data warehouse.

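### The Month 6 primary outcome accepts remission within 6 months and attributes this to ADVOCATE, whose endpoint the protocol itself gives as remission at Month 6

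*Protocol*

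**What the plan says.** The Month 6 primary outcome has two components: glucocorticoids and remission. The Summary Table of Study Protocol and the Analysis 3 panel of the Study Design Schema both tie the glucocorticoid component to Month 6 but give remission a window: "1 month before Month 6 and disease remission within 6 months of avacopan initiation". The endpoint table under Research Question and Objective(s) repeats this and adds an attribution: "disease remission (based on a BVAS v3 of 0) within 6 months of avacopan initiation, as defined in ADVOCATE".

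Other parts of the protocol use a time point:

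- Study Background and Rationale describes the first ADVOCATE primary endpoint as "clinical remission at Month 6, defined as achieving a Birmingham Vasculitis Activity Score version 3 (BVAS v3) of 0 and not taking glucocorticoids", with the glucocorticoid condition covering the month before Month 6.
- The follow-up dates under Treatment Outcomes include "6 months after avacopan initiation (for primary outcomes at Month 6".
- The Analysis 3 outcome list under Variables has "Remission at Month 6 (BVAS v3 = 0".
- The sustained-remission outcome in the Summary Table is "defined as remission at Month 6 and remission at Month 12", with further conditions on glucocorticoids before Month 12 and on relapse.
- The endpoint table lists "Complete remission at Month 6" as a separate bullet under the same objective. The available text does not say what makes remission complete or how this bullet differs from the outcome at issue.

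**The concern.** A patient can be in remission within 6 months without being in remission at Month 6. The window wording asks only that BVAS v3 reached 0 by Month 6. The time-point wording asks that it be 0 at Month 6. The protocol attaches the name ADVOCATE to the first, although its own background section attributes the second to that trial.

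Three things are at stake. First, the wording decides which patients count as successes in a primary outcome, and two chart abstractors could classify the same patient differently. Second, the result would carry the label of a phase 3 endpoint that it does not match, so a reader would set it beside the trial's figure as like with like. Third, the two primary outcomes would not share a Month 6 state, so a patient could succeed on the first and fail the Month 6 part of the second because of the same score.

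**Working it through.** The protocol states no figure that depends on this wording, so there is none to reproduce. The check compares the two rules and then asks what the document's numbers can say about size.

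**The two rules.** Let G mean that the patient took no glucocorticoids for GPA/MPA in the month before Month 6.

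- Window rule (Summary Table, schema and endpoint table, read literally): G, and BVAS v3 of 0 at some assessment up to and including Month 6.
- Time-point rule (ADVOCATE as the background section gives it): G, and BVAS v3 of 0 at Month 6.

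**Direction.** Anyone who meets the time-point rule also meets the window rule. The converse fails. For the same patients and the same G, therefore:

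proportion (window) − proportion (time point) = k / n ≥ 0

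Here n is the number evaluable at Month 6. The count k covers patients who reached 0 earlier, have activity again at Month 6, and meet G.

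**An example.** A patient scores 0 at Month 3, has activity again at Month 6, and took no glucocorticoids in the last month.

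- Window rule: success.
- Time-point rule: failure.
- Sustained remission at Month 12: failure, because its Month 6 part is not met.

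Nothing in the window wording excludes this patient.

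**Can such patients occur?** The endpoint table counts relapses from after Month 1. Study Feasibility and Futility Considerations reports 23 relapses among the 112 initiators and says that most patients stopped glucocorticoids within 2 months. Renewed activity before Month 6 in a patient off glucocorticoids is therefore possible. Activity too slight to meet the relapse rule, such as one minor item at a single visit, would also take the score off 0.

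**Size.** With n = 112, one such patient adds 1/112 = 0.0089, or about 0.9 percentage points. The document does not give k. It does not time the relapses, does not say how many fell before Month 6, and does not say how many initiators have a Month 6 assessment. If fewer than 112 are evaluable, each patient weighs more than 0.9 points.

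**Is the window wording just loose phrasing for Month 6?** Two features of the text suggest a real difference. The same sentence anchors glucocorticoids to Month 6 but gives remission a span. The endpoint table also has a separate bullet for remission at Month 6, which would be hard to explain if both meant the same thing. Against this, the label naming ADVOCATE and the follow-up date for the Month 6 primary outcomes point to the time point. The text does not settle the matter.

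**The case against.** The strongest reply is that no passage says remission at any time is enough. The endpoint table refers to ADVOCATE, the background section places that endpoint at Month 6, and the follow-up dates do the same for this study's primary outcomes. A reader who follows those pointers would assess BVAS v3 at Month 6, and both primary outcomes would then share that state. This stands in part. A reader might infer that the protocol has adopted an any-time rule and that patients active again at Month 6 will count as successes. The documents support only that they could, under the literal wording. Only the abstract-level text is available, and the blacked-out sections may say more.

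A reader might also infer that three rival versions of the outcome stand side by side. That overcounts. The background passage describes another trial, and the entry under Variables is a short item in a list that does not mark which outcomes are primary and lists glucocorticoid exposure separately. That entry may correspond to the complete-remission bullet. What remains is one study wording, in three places, that conflicts with its own label and with the time-point references elsewhere.

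It is tempting to size the effect from the relapses, for example 23/112 = 20.5 points as a ceiling, or some assumed share of it. The documents do not support this. The 23 are events, not stated to be distinct patients, and they cover all follow-up to January 2024. Those after Month 6 are irrelevant to the Month 6 score. A patient given glucocorticoids for renewed disease in the last month already fails G. Activity below the relapse rule is not among the 23, so 20.5 is not a ceiling either.

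Finally, Hypothesis(es)/Estimation says that outcomes will not be tested. No error rate or sample size depends on this proportion, and the visible text plans no formal comparison with ADVOCATE. That is true, but in a descriptive study the proportion is the result. The separate Month 6 bullet softens the harm, since a time-point figure may also be reported, but it does not correct the label on this outcome.

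**Conclusion.** The point holds as an internal contradiction with a wrong label. The stated Month 6 primary outcome uses a remission window and credits it to ADVOCATE, while the protocol's own account of that endpoint, and its other references to the Month 6 outcomes, use the time point. Read literally, the stated rule can only give a proportion equal to or higher than the time-point rule, for the same patients and the same glucocorticoid condition. The inflation may be zero. Its size is unknown: about 0.9 points per affected patient, assuming all 112 initiators are evaluable at Month 6. The finding does not rest on the relapse count. It should be corrected because it decides who is a success in a primary outcome and what that outcome may be called.

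**What to change.** In the Summary Table, the Analysis 3 schema and the endpoint table, define the outcome once: BVAS v3 of 0 at Month 6 and no glucocorticoids for GPA/MPA in the month before Month 6. Use the same state, by reference, as the Month 6 part of sustained remission.

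Align the remission entry under Variables with that definition. Either merge the complete-remission bullet for Month 6 into this outcome or state how it differs, so that the correction does not leave two bullets for one outcome.

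If remission reached at any time within 6 months is of interest, report it as a separately named descriptive outcome without the label naming ADVOCATE. Deleting the label alone would cure the misattribution but would leave the two primary outcomes with different Month 6 states.

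The cost is wording in a few places. The reported proportion may be slightly lower.

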### **Study Design/Type**

This is a retrospective cohort study (chart review)

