### **Data Analysis**

- The primary and secondary outcomes will be analyzed using a descriptive approach. Summary statistics for continuous variables, including the number of patients, mean, standard deviation (SD), median, Q1, Q3, minimum and

maximum, will be calculated after excluding missing/unknown values. For categorical variables, the frequency and percentage will be provided, and a category of “missing/unknown” will be included. Cumulative incidence will be used to describe the occurrence of key outcomes, including glucocorticoid toxicities, infections, and relapse. Given the variable follow-up time, healthcare resource utilization (HCRU) and costs will be presented as per patient per month (PPPM) metrics. Time to event outcomes (e.g., time to discontinuation of glucocorticoids) will be calculated using Kaplan-Meier analysis and median follow-up time (interquartile range [IQR]) will be reported.

- Among avacopan users, we will consider analyses evaluating time to events (e.g., glucocorticoid discontinuation, relapse) with adjustment for covariates. We will consider Cox proportional hazard regression models or other methods for time to event analyses and incorporate covariates, considering the number of observed outcomes. Restricted mean survival time will be used to describe time free from glucocorticoid exposure during follow-up.
- Among avacopan users, exploratory analysis of the association of glucocorticoid exposure with the risk of relapse will be assessed using an emulated target trial framework with a clone, censor, weighting approach. Cluster analysis will be used to explore patterns of glucocorticoid prescribing for patients using avacopan. Cox proportional hazards models will be used to evaluate factors associated with the risk of relapse and factors associated with glucocorticoid discontinuation.

CCI

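### In the glucocorticoid–relapse analyses, flares of one or two minor items must be seen at two consecutive visits, so treatment at the first visit can stop them being recorded

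*Protocol*

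**What the plan says.** In the Protocol, section Research Question and Objective(s), relapse is a return of vasculitis activity after improvement, assessed after Month 1. Two legs have no persistence requirement: "at least one major BVAS/WG item, at least three minor BVAS v3 items". The third requires persistence: "one or two minor BVAS v3 items for at least two consecutive clinical visits (ADVOCATE definition". The Variables section repeats the rule for the Analysis 3 outcomes ("one or two minor BVAS v3 items for at least two consecutive clinical visits"). Neither place sets an interval between the two visits or says how to handle a flare that was treated and had cleared by the second.

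This definition is the endpoint for the secondary objective "To evaluate the association of glucocorticoid use patterns with relapse risk in patients who initiate avacopan". The exposure is recorded after initiation and changes over time; the follow-up items under Treatment Outcomes include "Date of glucocorticoid discontinuation and usage patterns, including dosage changes". Under Data Analysis, "exploratory analysis of the association of glucocorticoid exposure with the risk of relapse will be assessed using an emulated target trial framework" with cloning, censoring and weighting, and Cox models are planned for factors associated with relapse. Under Study Design/Type: "This is a retrospective cohort study (chart review". Visits therefore follow routine care.

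**The concern.** Take two patients with the same flare of one minor item at the same visit. In the first, glucocorticoids are started or raised, and the item is gone at the next visit: no relapse. In the second, treatment is unchanged and the item is still present: relapse. The vasculitis activity at the first visit was identical. The recorded outcome differs because of the exposure under study.

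This is outcome misclassification that depends on exposure. Weighting and covariate adjustment deal with confounding and informative censoring; they cannot restore events that the definition never recorded. If glucocorticoids clear minor flares sooner, patterns with ready restarts will look protective even when the true flare risk is equal.

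**Working it through.** **Figures in the protocol.** There are 112 initiators and 23 relapses (Study Sample Size); 23/112 = 20.5% if each relapse is a different patient. The split by leg is not given, and there is no power or precision figure to reproduce. Everything below is illustration on assumed inputs.

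**Check 1: treated against untreated flares, true ratio 1.00.** Let m be the share of all flares with only one or two minor items, and r1 and r0 the probability that such a flare is gone by the next visit with and without glucocorticoid treatment. Recorded ratio = (1 − m·r1)/(1 − m·r0).

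| m | r1 0.5, r0 0.2 | r1 0.8, r0 0.2 | r1 0.8, r0 0 |
|---|---|---|---|
| 0.10 | 0.97 | 0.94 | 0.92 |
| 0.25 | 0.92 | 0.84 | 0.80 |
| 0.50 | 0.83 | 0.67 | 0.60 |

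If r1 = r0, the ratio is 1.00 for any m.

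**Check 2: two glucocorticoid patterns that treat different shares of flares.** Assume identical 12-month risks in both: 10% for the single-visit legs and 15% for flares of one or two minor items. Let f be the share treated at the first visit, and c_t and c_u the clearance before the next visit if treated or untreated. Recorded risk = 0.10 + 0.15·[f(1 − c_t) + (1 − f)(1 − c_u)].

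- Largest distortion: f 0.8 against 0.2, c_t 0.8, c_u 0.1. Risks are 0.10 + 0.15 × 0.34 = 0.151 and 0.10 + 0.15 × 0.76 = 0.214; ratio 0.71.
- Smallest: f 0.7 against 0.3, c_t 0.6, c_u 0.3. Risks are 0.10 + 0.15 × 0.49 = 0.1735 and 0.10 + 0.15 × 0.61 = 0.1915; ratio 0.91.

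On the minor leg alone these are 0.34/0.76 = 0.45 and 0.49/0.61 = 0.80. The inputs put 15/25 = 60% of flares in the affected leg, which nothing in the protocol supports.

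**Check 3: flares that could be missing.** If 23 are recorded and c is the overall probability of clearing by the next visit, unrecorded flares = 23/(1 − m·c) − 23. This gives 0.5 at m 0.10, c 0.2, and 15.3 at m 0.50, c 0.8.

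**Check 4: visit spacing.** With exponential flare duration of mean 8 weeks and fixed spacing d, a flare already seen at one visit is still present at the next with probability exp(−d/8): 78%, 61% and 22% for d = 2, 4 and 12 weeks. So confirmation also depends on the visit interval, which the protocol does not fix.

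**Check 5: candidate remedies on the Check 2 model.**

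- Counting a minor flare when glucocorticoid was started or raised, or when it persisted: recorded risk = 0.10 + 0.15·[f + (1 − f)(1 − c_u)]. With c_u 0.3 and f 0.8 against 0.2, this is 0.241/0.214 = 1.13. With c_u 0.1 and f 0.7 against 0.3, it is 0.2455/0.2395 = 1.03. The bias changes direction.
- Single-visit legs only: 0.10/0.10 = 1.00.
- Any return at a single visit: 0.25/0.25 = 1.00.

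**The case against.** The definition is a deliberate, labelled choice that allows comparison with ADVOCATE. The target-trial analysis is called exploratory, and the Hypothesis(es)/Estimation section excludes hypothesis tests of outcomes. With 23 events split equally, the standard error of a log ratio is about √(4/23) = 0.42, larger than the 0.35 shift at the extreme ratio of 0.71. Parts of the document are redacted, and the glucocorticoid strategies and censoring rule are not visible. Sensitivity definitions often belong in a statistical analysis plan, which is not at hand.

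Most of this stands as a limit on weight. It supports keeping the definition and does not justify replacing it. It does not remove the problem: the association is a listed secondary objective and will be estimated, the protocol itself fixes the endpoint for it, and imprecision does not excuse a bias of foreseeable direction. The hidden censoring rule matters too. If a restart at the first visit censors a clone assigned to stay off glucocorticoids, even a flare confirmed at the second visit would be lost from that arm.

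A reader might also infer from visit spacing that only 69%, 48% or 12% of flares are captured with visits every 2, 4 or 12 weeks. Those figures include flares never seen at any visit (48% of them at 12 weeks), which the two-visit rule does not cause. The model also takes spacing as unrelated to the flare; early recall after a flare would raise confirmation.

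**Conclusion.** The point holds for one leg of three, in the glucocorticoid–relapse analyses. On that leg ascertainment depends on the exposure, and no visible text or planned method corrects it. The direction, towards a protective appearance for ready restarts, assumes that treatment speeds clearance. The size is unknown; 0.60 to 0.97 is the range under assumed inputs, not an estimate for this cohort.

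Three stronger readings are not supported:

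- That glucocorticoid use decides whether relapse in general is recorded. Flares with a major item or at least three minor items count at one visit whatever the treatment.
- That the baseline-factor Cox models are biased in the same way. Their covariates are fixed before any flare, so bias would need a further link between a baseline factor and treatment readiness or visit frequency, which the protocol does not show.
- That the Month 12 sustained-remission outcome is wrongly defined. A minor flare after Month 6 that is treated and cleared can indeed pass, since glucocorticoids are barred only in the month before Month 12. But that outcome follows the trial's definition and is reported descriptively, without glucocorticoid pattern as the exposure.

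This is a worthwhile, inexpensive improvement, not a fault that invalidates the plan.

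**What to change.** Keep the protocol's definition as the main reported relapse outcome and report relapse counts by leg. For the glucocorticoid–relapse analyses, add two sensitivity outcomes that need neither a second visit nor a treatment decision:

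- (i) at least one major item or at least three minor items only;
- (ii) any return of one or more items at a single visit, dated at that visit.

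Do not replace the main definition with one that counts a flare because glucocorticoid was started or raised. That builds the exposure into the outcome and reverses the bias (Check 5).

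The cost is a few derived flags from the BVAS items already needed to apply the current rule. The downside is that (i) has fewer events and (ii) is less specific, so both should be shown beside the count under the protocol's definition. Neither recovers flares that fall between visits and are never seen.
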